The primary recruitment site for both aims will be Lumumba Sub-County Hospital (“Lumumba Clinic”), which is located next door to the RCTP. PrEP is included in the Kenyan National HIV Prevention Revolution Road Map [34], in which young women are identified as a priority population, and available at no charge through Lumumba Clinic and other public facilities. A total of 438 young women have received PrEP at this facility, making recruitment highly feasible. Contraception and STI testing/treatment (typically in the setting of symptoms, not routine screening) are also available free of charge. Recruitment may also occur through Kisumu County Hospital, which has a similar clinic and is located a 5 minutes-drive from our study offices.

Aim 1. Develop the *PrEP My Way* intervention

Overview. Using a client-centered approach, we will create a young woman-centered kit consisting of HIV self-testing, PrEP refills, STI self-sampling, and pregnancy tests and contraception (if desired), along with educational materials and kit delivery protocols for peer delivery in the community. We will hold individual interviews and focus group discussions with Kenyan women (age 16-24) in an iterative manner to optimally design *PrEP My Way* (the kit with instructional materials) and peer delivery system (including phone-based communication and kit delivery plans).

The intervention. *PrEP My Way* will be developed through an iterative, client-centered process. However, we anticipate that it will involve one clinic-based visit to safely initiate PrEP and contraception per Kenyan national guidelines [35], followed by quarterly community-based peer delivery of a pre-packaged, visually-appealing kit with pictorial and video guidance (to be

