Recruitment. We will identify young women to participate in the pilot RCT at the time they initiate PrEP at the Lumumba Clinic or Kisumu County Hospital. Participants may also be identified in the nearby community and invited to attend either facility to initiate PrEP and enroll in the study. Community recruitment will be done in areas such as hotspots, fish landing points, and within the general low end estates with the help of community health volunteers. These participants will be distinct from those engaged in the development of the intervention (Aim 1) to increase likelihood of generalizable findings. Similar to Aim 1, participants will be approached randomly (e.g., the second client seen on a given day) with stratification by age (16-20 versus 20-24). Only up to three participant will be enrolled per site per day to avoid clustering effects, as young women often present for PrEP services in groups [40].

Figure 4. Participant flow for the pilot RCT of *PrEP My Way* versus standard of care

Consent, enrollment, and randomization. Eligibility criteria for the pilot RCT participants are as follows. All participants will have started PrEP within the past two weeks:

- Inclusion criteria
 - Young woman (age 16-24 years); we will enroll emancipated minors (e.g., those who have not yet attained the age of legal competency as defined by state law, but who are entitled to treatment as if they had by virtue of assuming adult responsibilities, such as self-support, marriage, or procreation) per Kenyan national guidelines [39] or 16-17 year-olds with parental/caregiver consent
 - Initiating PrEP (this criterion subsumes all necessary safety assessments for starting PrEP, including HIV-negative status, normal renal function, and lack of Hepatitis B infection)
 - Reported sexual activity in the past 3 months
 - Residence in the Kisumu region (maximum of 20 km from our study offices at RCTP)
 - Phone ownership
 - Ability to understand KiSwahili, DhoLuo, and/or English

- Exclusion criteria- inability to provide informed consent (e.g., intoxication, mental disability)

Note: Participants may also be excluded at the discretion of the principal investigator (e.g., because of co-enrollment with a study that would compromise study aims or disruptive behavior).

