Participants will be consented as described in Aim 1, enrolled, and randomized (1:1) using a computer-generated simple randomization sequence to receive *PrEP My Way* or follow up as usual at Lumumba Clinic or Kisumu County Hospital over the next 6 months. The code creating the random allocation order will be generated and maintained by the study analyst (separate from the investigators). A variable size block randomization scheme will be implemented to produce the randomization list. Randomization will be implemented by transcribing onto paper within numbered envelopes. Thus, neither participants nor study staff will be blinded to each participant's randomization arm assignment. Fidelity of randomization will be confirmed with tracking in REDCap.

Study procedures (Some aspects of the planned procedures may change pending input from Aim 1 findings). Study procedures for both arms are summarized in Table 1.

Table 1. Summary of study procedures by arm. Each cell indicates how/where the procedure will take place.								
	M0	M1	M3	M6	M0	M1	M3	M6
	PrEP My Way				Control			
Education (PrEP, sexual health)	Clinic	Peer	Peer	Peer	Clinic	Clinic	Clinic	Clinic
HIV testing	Clinic	Kit	Kit	Kit	Clinic	Clinic	Clinic	Clinic
PrEP	Clinic	Kit	Kit	Kit	Clinic	Clinic	Clinic	Clinic
STI sampling	Clinic [^]	Kit	Kit	Kit	Clinic [^]	Clinic [^]	Clinic [^]	Clinic [^]
Pregnancy testing; contraception	Clinic	Kit	Kit	Kit	Clinic	Clinic	Clinic	Clinic
Questionnaire administration	RA	--	--	RA	RA	--	--	RA
Acceptability scale and interview	--	--	--	RA	--	--	--	--
DBS	--	--	--	RA	--	--	--	RA

Clinic=Lumumba Clinic or Kisumu County Hospital; [^]STI testing done only in the setting of symptoms; RA = research assistant; time and motion studies will also be done at the KEMRI Research Care and Training Program (i.e., the study site), Lumumba Clinic, and Kisumu County Hospital mid-way through the study period

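### The allocation sequence is described as both simple and blocked, and the plan does not say whether facility or age stratifies it

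*Combined protocol and SAP*

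**What the plan says.** The paragraph on consent, enrollment and randomization under Aim 2 describes the sequence twice. Participants are "randomized (1:1) using a computer-generated simple randomization sequence". Two sentences later, "A variable size block randomization scheme will be implemented to produce the randomization list". The mechanism follows: "Randomization will be implemented by transcribing onto paper within numbered envelopes". The paragraph gives no block sizes and no stratification factor, and does not say whether there is one envelope series or one per facility. The list is held by an analyst separate from the investigators, the trial is open-label, and REDCap tracks adherence to the list.

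The Recruitment paragraph under Aim 2 says women are identified "at the time they initiate PrEP at the Lumumba Clinic or Kisumu County Hospital", with at most three enrolled per site per day. It also says they are approached "with stratification by age (16-20 versus 20-24" years). That sentence concerns how women are approached. It does not mention allocation, and a woman aged 20 fits both bands.

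On the weight of each facility, the Study setting text says "The primary recruitment site for both aims will be Lumumba Sub-County Hospital". It presents Kisumu County Hospital as a possible further source with a comparable clinic, a short drive from the study offices. The expected share from each is not given.

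The Analysis section compares the two primary outcomes between arms with chi-square tests. Its supporting logistic models list age among the pre-specified variables. Facility is not listed.

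**The concern.** Simple randomisation makes each assignment independently, so arm sizes float. Permuted blocks constrain arm sizes. An analyst cannot build a list that satisfies both descriptions, and a later report could not state the method accurately from this text.

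The second question is what the list balances. Unstratified blocks balance only the arm totals. The plan treats age as important enough to stratify recruitment and to enter the regression models. Facility matters for a different reason: control participants receive their care there, and control-arm retention, a primary outcome, is read from clinic records. If neither factor stratifies allocation, their balance is left to chance in a small trial. For facility, no listed model would then adjust for an imbalance.

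**Working it through.** **Inputs from the documents.** Up to 150 randomised 1:1, so 75 per arm. Loss of 20%, so 0.8 × 75 = 60 per arm analysed. The Power section rests on 80 evaluable, which implies 80/0.8 = 100 randomised, or 50 per arm. Planning rates are 40% versus 60%.

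**Assumptions, because the documents give no figure.** Half of participants in the younger age band; 30% at the second facility; an outcome gap of 10 to 30 points between levels of a factor; two-sided 5% tests.

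**The plan's own figure.** The documents give no figure for balance. The nearest is the power of about 40% with 80 evaluable. A pooled normal calculation at 40 per arm gives 43.1%, and the usual two-sided variants run from 34% to 46%. That is consistent with a rounded value, and nothing below depends on it.

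**Step 1: what the simple/blocked conflict changes.**
- Simple randomisation of 150: one arm's 95% range is 63 to 87. The chance of a 67/83 split or worse is 22% (exact binomial).
- One unstratified list of variable blocks (sizes 4, 6 and 8 assumed; 5,000 simulated trials): the arms differ by at most 2 in 95% of trials, and by 4 at most.
- Power cost of unequal arms: 43.1% at 40/40, 41.7% at 32/48, 40.9% at 30/50. This is small.
- Covariate balance hardly changes. At 150 randomised, the chance of an age imbalance of 10 points or more is 21.5% under simple and 22.2% under unstratified blocks. At 100 it is 32.0% and 32.9%.

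**Step 2: chance imbalance without stratification.** The SD of the between-arm difference in a factor's share is √(2q(1−q)/n), where q is the share and n the number per arm. The chance of 10 points or more is 2(1 − Φ(0.10/SD)).

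| n per arm | Age, q = 0.5: SD | Chance | Facility, q = 0.3: SD | Chance |
|---|---|---|---|---|
| 75 | 0.082 | 22% | 0.075 | 18% |
| 60 | 0.091 | 27% | 0.084 | 23% |
| 50 | 0.100 | 32% | 0.092 | 27.5% |

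At 75 per arm, the chance that at least one factor is out by 10 points is 1 − (1 − 0.221)(1 − 0.181) = 36%, taking the factors as independent. The facility figure depends on the assumed share. At q = 0.1, SD = √(2 × 0.1 × 0.9/75) = 0.049 and the chance is about 4%. At q = 0.5 it equals the age figure, 22%.

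**Step 3: what an imbalance would do.** The shift in the risk difference is imbalance × outcome gap. For a 10-point imbalance: 0.10 × 0.10 = 1 point, up to 0.10 × 0.30 = 3 points. The standard error at 60 per arm is √(2 × 0.24/60) = 0.089, about 9 points. The shift is therefore about 0.1 to 0.3 standard errors.

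**Step 4: precision available.** The share of outcome variance explained by a factor split 50/50 with gap g is about 0.25g²/0.24. For g = 0.10 this is 1%; for g = 0.30 it is 9%. In the latter case the standard error falls from 8.9 to 8.9 × √0.91 = 8.5 points.

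**Step 5: effect of stratifying.** Under the same assumptions, with blocks stratified by facility and age, the SD of the age difference at 150 randomised falls from 0.082 to 0.015, and the chance of a 10-point age imbalance from 22% to about 0%. Arm totals stay within 4 in 95% of trials (maximum 8). Facility balance was not tabulated, but the same constraint acts on it.

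**The case against.** The strongest case is that this is a wording slip in a pilot. The only sentence on how the list is produced specifies blocks, so the stray word is probably simple. Unstratified allocation is a legitimate choice in a study that describes its power as limited and says effectiveness is not its aim. All of this stands, but the text still contains two methods and needs one.

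Four stronger readings are tempting, and the documents do not support them.

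- A reader might infer that the conflict itself leaves the arms unbalanced on covariates. Step 1 shows otherwise: it affects arm sizes, at little cost in power.
- A reader might infer that facility and age drive the outcomes, so that the comparison is biased. No outcome gap by either factor is given, and the second clinic is described as comparable. Chance imbalance under valid randomisation is already covered by the standard error and does not raise type I error.
- A reader might infer that age is ignored. It stratifies recruitment and is in the supporting models. What is missing is a statement about allocation.
- A reader might infer that a single run of envelopes must be shared between two facilities. The plan says neither that there is one run nor where it is held. Both facilities are close to the study offices, so one centrally held series is possible.

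Stratifying also has a cost. In an open-label trial, small strata make the next assignment somewhat easier to guess.

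**Conclusion.** The contradiction between simple and blocked randomisation and the overlap at age 20 are plain in the text and need no assumption. The plan also leaves open whether age or facility stratifies allocation and how envelopes are organised across facilities. The consequence is chance imbalance and modest lost precision: about a 22% chance of a 10-point age imbalance and 18% for facility at 75 per arm. A 10-point imbalance would shift the effect by 1 to 3 points, set against a standard error of about 9. The first pair of figures rests on the assumed 50/50 and 70/30 splits, and the shift on the assumed 10 to 30 point gap. Validity is not in question. The correction is worth making because the allocation rule cannot be followed as written and the remedy is cheap.

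**What to change.** In the randomization paragraph, delete the word simple. State variable-size permuted blocks with undisclosed sizes, stratified by facility (Lumumba, Kisumu County Hospital) and by an age band with no overlap, for example 16–19 and 20–24. Use the same bands in the Recruitment paragraph. Provide a separate concealed envelope series, or REDCap list, for each of the four strata.

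In the Analysis section, report a primary comparison adjusted for facility and age, alongside or in place of the unadjusted chi-square test, and add facility to the supporting models.

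The cost is four short lists instead of one, a few sentences of text and slightly more envelope handling. Guessing of assignments in small strata becomes somewhat easier; variable, undisclosed block sizes limit this. Planned power does not change materially.

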At kit delivery, the peer will guide the participant through the pictorial materials for each aspect of the kit and show her the video. HIV test results will be available at the time of testing. The peer can be present to see the test results or not, per the participant's preference. She will answer any questions regarding the kit and its components; any challenging questions will be brought back to clinical staff at the RCTP study site and answers relayed to the participant via phone. The peer may also provide weekly empowerment messages (e.g., "Remember- PrEP gives you control over your sexual health") via phone; participants will be able to opt out of these messages, if desired (e.g., for privacy). The peer will obtain the HIV test results and document PrEP and contraception use. She will bring the vaginal swab back to the study site for processing. The peer will also dispose of any remaining materials, if desired by the participant. The peer will send an SMS or WhatsApp message indicating either normal results or the need for the participant to come to the study site for abnormal or indeterminate results within a few days. Explicit mention of STI testing will not occur in the messages to protect the participant's privacy of the participants. Treatment and supportive counseling will then be provided by our staff per Kenyan national guidelines [35]. Arrangements will be made for prompt repeat HIV testing at our study site if any of the self-testing kits reveal a positive or indeterminant result; linkage to free antiretroviral therapy services will be facilitated in the event of a confirmed seroconversion. Participants will be offered repeat STI testing in the clinic if their self-collected samples are inadequate for testing. Follow-up for any other concerning situations (e.g., social harms) will be arranged by study staff as appropriate (see *Human Subjects*).

[figure not shown]
At completion of the visit, the peer will make tentative plans for a repeat visit in two months (Month 3 of PrEP). She will remind the participant that she is available via mobile phone for any *PrEP My Way*-related questions and support. She will then contact the participant one week in advance of the tentative visit appointment to confirm it or make any necessary adjustments. Scheduling will aim to avoid any lapses in PrEP coverage and will occur in a private location during reasonable working hours, as described above.

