The above-noted procedures will be repeated at the Month 3 and Month 6 visit. Additionally, at the Month 6 visit, an RA will collect the following data either in the field or at the study site (within the next two weeks):

- Dried blood spot for tenofovir concentration
- Creatinine (point-of-care)
- Socio-behavioral data (quantitative questionnaire; see Table 1)
- Acceptability data (see below)

Acceptability will be determined quantitatively with the Systems Usability Scale (SUS; [49]). This 10-item Likert scale assesses domains including desired frequency of use, complexity, need for support, functionality, irregularities, ease of learning/use, time required for use, confidence, and training needed. Qualitatively, we will explore *PrEP My Way* in accordance with the Unified Theory of Acceptance and Use of Technology (UTAUT; Figure 5) in up to 20 participants purposively selected to

Figure 5. Unified Theory of Acceptance and Use of Technology

reflect high and low usage of the kits. Questions for each model component are described in Table 3.

All quantitative data will be recorded on encrypted tablets in REDCap. Qualitative interviews will be digitally recorded and transcribed. All data will be collected in a private space using the participant's preferred language (KiSwahili, DhoLuo, or English).

Table 3. Questions to be used in assessing PrEP My Way acceptability	
Model component	Question content
Performance expectancy	Perceived usefulness, personal outcome expectations
Effort expectancy	Perceived effort needed to arrange delivery and use the kit components
Social influence	Perceived norms and stigma
Facilitating conditions	Kit delivery, instructional materials, role of the peer
Behavioral intention to use	Attitudes around current and anticipated future use/non-use
Actual use	DBS tenofovir concentration

Participants will then be disenrolled from the study and linked back to the Lumumba Clinic, Kisumu County Hospital, or a similar clinic of their choice, for continuation of PrEP as desired. A small incentive/thank you gift (worth a minimum of ~500 Kenyan Shilling or \$5 US) will be given at that time for transport and completion of study-related activities (not *PrEP My Way* utilization). The estimated time spent with the participant will be ~2 hours at enrollment, 30 minutes at Months 1 and 3, and ~1 hour at Month 6.

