Control condition. After randomization, a study research assistant (RA) will administer the baseline demographic and socio-behavioral questionnaire. Control participants will then continue to receive PrEP and any other desired sexual health services at Lumumba Clinic or Kisumu County Hospital. The study may provide or assist the clinics in obtaining necessary supplies for routine HIV/STI services in the event of supply chain stock outs. The RA will call the control participant in ~3 months to maintain accurate contact information and remind her that the RA will meet her at her 6-month PrEP appointment in the Lumumba Clinic or Kisumu County Hospital for the final study visit. The RA will make a reminder call one week in advance. If the control participant does not wish to continue PrEP or return to the Lumumba Clinic/Kisumu County Hospital, she may come to the RCTP study site for the final study procedures. The RA will then collect the following using the methods described above:

- Dried blood spot for tenofovir concentration
- Socio-behavioral data (quantitative questionnaire)
- Review of Lumumba Clinic/Kisumu County Hospital chart records for HIV and STI testing and pick up of PrEP and contraception; participants may be asked for clarification if chart records are incomplete

Control participants will then be disenrolled and provided with a small incentive/thank you (worth at least~500 Kenyan Shillings or \$5 US) for completion of study-related activities. They will continue to receive PrEP and other sexual health services at Lumumba Clinic, Kisumu County Hospital, or another clinic as desired.

Peer identification and hiring, and oversight. Peers will not be participants. They will be identified from PrEP programs in the Kisumu region. Peers will be 18-30 years old women who have themselves taken PrEP for at least 3 months and are fluent in KiSwahili, DhoLuo, and/or English. If they do not own a smart phone, the study will provide one for showing the *PrEP My Way* video guidance and enabling two-way communication with participants (e.g., SMS, WhatsApp). Although already experienced with PrEP, all peers will be trained about PrEP using Kenyan national guideline materials [35]. They will also undergo sensitivity training, including

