Feasibility. Feasibility will be assessed by the following metrics: 1) receipt of the *PrEP My Way* kit at Months 1, 3, and 6, and 2) ability of the participant to use each aspect of the kit (i.e., the HIV self-test, use of the vaginal swab, and self-administration of medroxyprogesterone [if desired]) per protocol. The intervention will be considered feasible if $\geq 70\%$ (35/50) participants 1) receive a kit and 2) achieve a readable HIV test, usable vaginal swab, and self-injection of medroxyprogesterone, if desired, at $\geq 66\%$ (2/3) of visits.

Acceptability. The *PrEP My Way* intervention will be considered acceptable if $>70\%$ (35/50) participants rate 70% (7/10) items on the SUS as "very good" or higher. The qualitative interview will delve deeply into each of the four domains of the UTAUT model to provide in depth feedback on the intervention.

Primary outcomes- Preliminary impact on PrEP adherence and program retention at 6 months. PrEP adherence will be assessed primarily by DBS for tenofovir diphosphate (TFV-DP) concentration. The TFV-DP concentration will provide an estimate of doses taken over the prior 3 months (see Table 4; [11, 50]). Retention will be assessed by kit receipt in the intervention arm and clinic attendance per clinic records in the control arm at Month 6. Potential influencing and mediating socio-behavioral factors (Table 2) will be explored.

Secondary outcomes. We will assess the following:

Table 4. TFV-DP concentrations in DBS	
Estimated use	Median fmol/punch (IQR)

- Self-reported PrEP adherence at Months 1, 3, and 6 (intervention arm) and Month 6 (control arm). We will use the 3-item scale developed by Wilson et al, which involves different recall tasks (frequency, percent, and rating of adherence) over the prior 30 days [51]
- PrEP persistence over the 6-month period
- Rates of STI testing at Months 1, 3, and 6
- Rates of pregnancy test and contraception pick up at Months 1, 3, and 6
- Cost estimates

Protective*	>1,250
Moderate	900-1,249
Low	<900

*Exact value to be explored (see text)

Analysis

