Primary outcomes. Adherence (as determined by TFV-DP concentrations in DBS) and program retention at 6 months will be analyzed descriptively and then compared between the two study arms using Chi-square tests (i.e., comparing protective TFV-DP concentrations versus not; retained versus not). DBS will be shipped to the University of Cape Town in South Africa and some will be tested to measure TFV-DP concentrations. We will use an intention-to-treat approach for the primary outcomes but will also perform per protocol analysis. Because of the developmental nature of this R34 study and the small sample size, we will assess potential influencing factors on adherence and retention using logistic regression models. Thresholds from protective TFV-DP concentrations may be explored, as this is an active area of research [53, 54]. We will pre-specify variables to avoid overfitting the models as age, self-esteem, empowerment, stigma, depression, and alcohol/substance use. We will analyze study outcomes by peer to look for any clustering effects. We will also explore empowerment and depression as mediators of the relationship between the *PrEP My Way* intervention and adherence and retention outcomes, using the approach by Valeri and VanderWeele, which allows for logistic modeling, and sensitivity analyses around key assumptions per Imai.[55].

Secondary outcomes. We will use descriptive statistics to understand self-reported adherence, PrEP persistence, early retention, and rates of STI testing, pregnancy testing, and contraception pick up. We will also explore trends for self-reported adherence within the intervention group with regression analysis. We will compare all secondary outcomes between intervention and control arms with Chi-square tests (categorical variables) and t-tests (continuous variables). As described above, we will also explore in the influence of age, self-esteem, empowerment, stigma, depression, and alcohol/substance use on any observed differences through logistic and linear regression models, for dichotomous and continuous variables, respectively.

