Cost analysis will follow the Clinton Health Access Initiative guidelines for costing HIV interventions [56, 57] and will reflect the provider perspective. We will conduct activity-based micro-costing to estimate the costs of the *PrEP My Way* intervention; data will be collected from the study budget, clinic expense reports, published information on labor costs, and staff interviews. These data will be used to complete cost worksheets. Costs will be categorized as fixed or variable. Variable costs indicate which costs could change (e.g., using free communication instead of standard telephone rates) and influence the estimates from the study.

Power. We are estimating the power of the study sample based on PrEP adherence at 6 months. Based on prior studies (see Figure 2), we anticipate a 60% overall decrease in PrEP adherence from enrollment to Month 6. We estimate ~1/3 of that decrease will be due to appropriate rationale (e.g., no longer at risk for HIV acquisition or use of other HIV prevention methods such as condoms), in accordance with the concept of prevention-effective adherence [58]. We therefore believe 2/3 of a 60% decrease or 40% decrease is an ideal target for this

intervention. Of note, with prevention-effective adherence, PrEP adherence should be aligned with risk for HIV acquisition and lack of use of other effective means for HIV prevention. In this study, we will be following clients for the first six months of PrEP use. We are considering this period as a “season of risk” based on the client’s desire to initiate PrEP and will include the full six months in the denominator when calculating adherence and persistence. Future studies of *PrEP My Way* will include metrics of risk to determine prevention-effective adherence. We will, however, follow sexual behavior and reported risk to track the ongoing need for PrEP as a secondary analysis.

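### Contraception pick-up is compared between arms, but the plan describes peer-recorded use in the intervention arm and chart pick-up in the control arm

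*Combined protocol and SAP*

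**What the plan says.** All of this is in Aim 2 of the combined protocol and SAP.

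- **Intervention condition (kit delivery):** "The peer will obtain the HIV test results and document PrEP and contraception use". The step recurs later: "The above-noted procedures will be repeated at the Month 3 and Month 6 visit".
- **Control condition:** at the final visit the research assistant reviews "chart records for HIV and STI testing and pick up of PrEP and contraception". The only back-up is that "participants may be asked for clarification if chart records are incomplete".
- **Outcome measures, Secondary outcomes:** "Rates of pregnancy test and contraception pick up at Months 1, 3, and 6". The same list includes "PrEP persistence over the 6-month period", with no definition or source.
- **Analysis, Secondary outcomes:** "We will compare all secondary outcomes between intervention and control arms with Chi-square tests (categorical variables) and t-tests (continuous variables".
- **Power:** the plan "will include the full six months in the denominator when calculating adherence and persistence". This fixes a denominator for persistence but not what is counted.

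**The concern.** The outcome is pick-up, yet the plan describes a record of contraception pick-up only in the control arm. Use and pick-up can differ for the same woman at the same visit. A woman still covered by an earlier supply is a user with nothing to collect. A woman who takes a method from the kit and leaves it unopened has picked up but is not a user. The mismatch therefore arises even if every chart is complete and every woman stays in her assigned channel.

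At stake is whether a between-arm difference in contraception, or the lack of one, says anything about the intervention. The protocol presents this pilot as a step towards a full trial, so a difference produced by the recording method could be carried forward as a signal.

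**Working it through.** **1. The records side by side**

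| | Intervention | Control |
|---|---|---|
| Recorder | Peer, at Months 1, 3 and 6 | Research assistant, from the chart at Month 6 |
| Contraception item described | Use | Pick-up |
| Outcome to be compared | Pick-up | Pick-up |

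**2. Does anything else in the plan supply a common measure?**

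- Kit receipt is recorded, but it serves feasibility and retention. Contraception in the kit is optional (Aim 1, Overview), so receiving a kit does not show that a contraceptive was taken.
- Table 1 shows where contraception is provided, not what is recorded.
- Table 2, the questionnaire given to both arms, lists condom use and no other method.

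Nothing in the text closes the gap.

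**3. How large could the effect be?** The plan has no figure on this point to reproduce, so what follows is an illustration.

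Inputs:

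- From the Power section: 80 analysed, which at 1:1 gives n = 40 per arm.
- Assumed: two-sided 5% test; true use u, the same in both arms; a share s of control users with no supply due at the visit.

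The intervention arm is then recorded at u and the control arm at u(1 − s). With a and b the recorded counts, the Pearson statistic is X² = 2n(a − b)² / [(a + b)(2n − a − b)]. The rejection rate is the sum of the binomial probabilities of all pairs (a, b) with X² > 3.841.

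Example: u = 50% and s = 1/3 gives 50% against 0.50 × 2/3 = 33.3%, and rejection in 33.9% of trials.

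False rejection at one visit, n = 40 per arm:

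| True use u | s = 0 | s = 0.1 | s = 0.2 | s = 1/3 | s = 1/2 |
|---|---|---|---|---|---|
| 20% | 5.1% | 5.7% | 7.7% | 12.8% | 24.7% |
| 30% | 4.8% | 5.9% | 9.1% | 17.7% | 36.6% |
| 40% | 5.2% | 6.6% | 11.4% | 23.9% | 49.7% |
| 50% | 5.7% | 8.1% | 15.7% | 33.9% | 64.7% |

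A larger sample makes this worse. With 150 enrolled and 20% lost, n = 150 × 0.8 / 2 = 60 per arm, and the case u = 50%, s = 1/3 rises from 34% to 47%.

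**4. The opposite direction.** Suppose true pick-up is 50% in both arms, but the peer records use, which is a fraction r of pick-up because some supplies are not used. With r = 0.9 the comparison is 45% against 50% (−5 points); with r = 0.6 it is 30% against 50% (−20 points). The same enumeration gives false rejection of 8% and 46% (7% and 45% by the normal approximation). Here the intervention arm looks worse.

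**The case against.** The best defence is that *use* is loose wording. The sentence sits among the practical steps of a kit visit and may mean what the woman took from the kit. The outcome list names one measure, pick-up, for both arms. The study supplies the kits, so it is placed to know what was handed over, and the protocol allows procedures to change after Aim 1. This is a fair reading, and it is why the point is conditional on the text as written. It does not remove the point: no dispensing record is described, and a form built from that sentence would ask about use.

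Three further objections stand and limit the claim.

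- **Direction.** A reader might infer that the intervention arm will look better. That requires the peer to count methods already in hand and control women to be often between supplies. The documents state neither, and step 4 of the working shows the reverse is possible.
- **PrEP persistence.** A reader might infer that it suffers the same mismatch. The peer does document PrEP use, and the control chart does show PrEP pick-up. But persistence has no stated source, and kit receipt or self-report could equally feed it. The documents support only that the source must be specified.
- **Size.** The larger rejection rates need a third to a half of users to have no supply due. At one tenth to one fifth the rates are about 6% to 16%.

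It is also true that this is one secondary outcome in a pilot that does not aim to show effectiveness. That limits its weight, but the plan still chose to test it between arms.

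**Conclusion.** The point holds for contraception pick-up. As written, the plan compares peer-recorded use with chart-recorded pick-up, and a difference between arms could not be attributed to the intervention. The bias can run either way.

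Its size cannot be fixed from the documents. Under assumed use of 20% to 50%, 40 women per arm and a two-sided 5% test, false rejection in the case where control users are between supplies runs from about 6% (one tenth not due) to 65% (half not due).

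The point does not extend to the primary outcomes. Adherence is measured by dried blood spot in both arms, and Month 6 retention uses kit receipt and clinic attendance; neither draws on these contraception records. For PrEP persistence the conclusion is only that a definition and source are missing. This is worth correcting before data collection, because what was dispensed may not be recoverable from a form that recorded only use.

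**What to change.** 1. Add to the kit form a line for each contraceptive handed over: type, quantity and date. Extract the same three fields from control charts, including what was dispensed at the Month 0 clinic visit in both arms.
2. Define the outcome as the same event over the same windows in both arms (enrolment to Month 1, Month 1 to 3, Month 3 to 6), for example any pick-up or days covered by supply in each interval. A yes/no at each visit is not enough: if kits and clinics supply for different lengths of time, it would still differ between arms when behaviour is identical. Days covered, calculated from the quantity supplied, deals with this most directly.
3. Report peer-recorded use descriptively, in the intervention arm only.
4. If current use is to be compared, add one identical current-contraception item to the questionnaire both arms already complete at baseline and Month 6.
5. State the data source for PrEP persistence. If it rests on these records, use one dispensing-based definition in both arms.

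The cost is a little more form completion at each delivery, some extra chart extraction and a few sentences in the outcome definitions. No visit, arm or element of care changes.
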